The definitive method of classifying SIB as *socially* maintained or *automatically* maintained is a specialized five- to six-hour assessment called a *functional analysis*. We intend to enrich the study sample with children classified with automatically maintained SIB based on the functional analysis. To minimize subject burden and to manage study resources, we want to avoid conducting the detailed functional analysis on subjects who do not get classified with automatically maintained SIB. We have developed a screening interview to aide in identification of subjects with automatically maintained SIB before undertaking the detailed functional analysis. Demonstrating a high positive predictive value is a necessary prerequisite for launching a larger study. Using the formula: Positive Predictive Value (PPV) = screen positive and true cases \div all positive screens, we set a benchmark of 75%. Information learned in the study will likely enhance our PPV for future studies.

NOTE: Children who are classified with socially maintained SIB will not be randomized. [name] will meet with the family to plan the next phase of treatment.

Aim #3. To evaluate the preliminary efficacy of NAC for reducing SIB in 14 children with ASD in a 9-week, double-blind, placebo-controlled, randomized trial.

This sample size is not sufficient to test the superiority of NAC over placebo. We use a randomized design to meet Aim #1 and to enable blinded assessment of outcome by an independent evaluator.

Preliminary efficacy benchmarks within the NAC group

- a) Significant decline from baseline to Week 9 on the parent-rated Aberrant Behavior Checklist Irritability subscale (commonly used parent-rated survey of tantrums, aggression, and self-injury).
- b) at least 50% decline (on average) from baseline to Week 9 in the number of SIB events in children treated with NAC when counted by a trained technician who is blind to treatment assignment.

c) at least 50% of the subjects on will be rated *much improved* or *very much improved* on the Improvement scale of the Clinical Global Impression by a clinician blind to treatment assignment.

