Pilot studies are not about efficacy (Leon et al., 2011). Before launching a larger **definitive** randomized clinical trial, we need to show that the study procedures and medication are acceptable to parents, that we can successfully recruit and retain children with moderate to severe repetitive SIB in a randomized trial, and that we can collect outcome data. Fourteen children with ASD will be enrolled and randomly assigned to NAC or placebo for 9 weeks. Enrollment will occur from Month 2 through Month 9 of the project (average at least 1.75 subjects per month). Children will be recruited through the Marcus Autism Center (from the current waitlist and referrals). Potentially eligible children will be screened by phone to confirm the presence of SIB that is moderate – but not in need of immediate service. Children with presumably moderate SIB will be invited to come to Marcus for a formal screening visit to confirm eligibility (see Table 2 for Schedule of Measures).

Table 2.0 – Schedule of Measures

Measures	Staff	Screen	FA Screen	Baseline	Study Week				
					1	2	4	6	9
ABC	RC	X		X			X		X
Adverse Event	MD	X		X	X	X	X	X	X
CGI-I	IE			X			X		X
CGI-S	IE	X		X			X		X
CGSQ	RC			X			X		X
Cognitive Test (Mullen or Stanford-Binet 5)	IE	X							
CYBOCS-ASD	IE			X			X		X
Demographic Form	RC	X							
Detailed Functional Analysis	IE/RC		X						X
Direct Observation Session	IE/RC			X					X
Drug Compliance	RC				X	X	X	X	X
DSM-V checklist	IE	X							
Functional Assessment Interview	IE	X							
Medical History	IE	X							
Parent Satisfaction Questionnaire	RC								X
Parent Target Problem	IE	X		X			X		X
Physical Exam	MD	X							
Research lab test**	RC	X							X
Responder Status	IE								X
Routine blood tests*	RC	X							X
Safety Review	MD	X		X	X	X	X	X	X
SCQ	RC	X							
Treatment Review and Planning	Clinic								X
Vineland III	RC	X							
Vitals, Height and Weight	RC	X		X			X		X

* CBC, electrolytes, BUN, creatinine, liver function tests

** see Aim 5 (drawn at same time points of safety labs)

Subject Characterization Subjects will be characterized in accordance with current practice at Marcus to confirm an ASD diagnosis and essential clinical characteristics (e.g., IQ, adaptive functioning, behavioral problem profile). For details, see Appendix A.

Inclusion criteria

1. Boys and girls ≥ 5 and ≤ 12 years 11 months
2. Confirmed diagnosis of ASD (clinical interview, Social Communication Questionnaire, DSM-V checklist)

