may occur for longer periods of time (such as hand biting). Real-time counts of SIB will be tallied by a trained rater (blind to treatment condition) during a set of structured, 10-minute conditions that will include routine demand, restricted access to tangible items, restricted access to attention, free play with free access to parent-identified preferred items, and when the child is left alone in an austere environment. The rater will also complete a 4-point severity rating scale of SIB (0=none, 1=mild, 2=moderate, 3=severe) for each condition. A skin check is performed following sessions with moderate levels of self-injurious behavior, which will document marks likely caused by the behavior observed in a session. The child's visible body parts (i.e., arms, face) and any targeted body parts (e.g., back, scalp) will be assessed. Data collectors will denote the severity rating based off of the skin checks. Per minute counts of SIB across the entire length of the observational period as well as per minute counts in different conditions (routine demands, restricted access to tangible items, restricted access to attention, free play, and alone in austere environment). An average of the 10-minute severity ratings will also be calculated at baseline and endpoint. Change in counts and the average severity score within the NAC group (paired t test) and across treatment groups (ANCOVA) will be used to evaluate preliminary efficacy. Counts and severity during the alone condition (automatically maintained SIB) will be analyzed separately.

Parent Target Problems At baseline, parents will be asked to nominate the two most important problems for the child. Through brief discussion, the frequency (for episodic behaviors) or constancy (for problems such as impulsiveness reflecting more enduring patterns), intensity and impact of the behavior on the family are established. Responses from this systematic inquiry are documented in a brief narrative. The narrative will be reviewed at Weeks 2, 6 and 9 and a new narrative documented. This review will assist with the scoring of the CGI-I in real time ([name] et al., 2015).

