Improvement item on the Clinical Global Impression scale (CGI-I) The CGI-I is a 7-point scale designed to measure overall improvement from baseline ([name] et al., 2015). Scores range from 1 (Very Much Improved) to 4 (Unchanged) to 7 (Very Much Worse). The CGI-I will be used to assess overall response to treatment. By convention, scores of Much Improved or Very Much Improved are used to define *positive response*; all other scores are classified as a *negative response*. Using available information (ABC scales, Parent Target Problems, Parent Daily Rating), the CGI-I will be rated by a blinded independent evaluator ([name]) trained by [name].

Aim #4 [Safety and Tolerance]

A blood sample for routine lab tests (CBC, BUN, creatinine, liver function panel) will be collected at screening and at endpoint. These lab results will be reviewed by [name] (Pediatric Nurse Practitioner) with consultation from Drs. [name] and [name] as needed. Clinically important findings will be shared with the family.

Adverse Events At each visit the treating clinician will ask specific queries about major body systems, activity level, sleep, appetite, and general health. The assessment will be guided by the Adverse Events Review. This measure will be conducted at baseline so that current health complaints are known and documented. New events, whether presumed related to treatment or not, are classified as an adverse event and rated as Mild, Moderate or Severe (See Appendix B for definitions).

Aim #5 [Biomarkers and Mechanism of Action]

In addition to the blood drawn for safety monitoring, we collect an additional tube (2 cc, lavender top) of whole blood to examine redox couples and amino acid neuromediator levels before and after NAC treatment. Samples will be centrifuged twice to obtain platelet-free plasma. These samples will be analyzed in [name] lab using ultra-sensitive, quantitative mass spectrometry methods (Tirouvanziam et al., 2006; Tirouvanziam et al., 2012; Hardan et al., 2012; Conrad et al., 2015). NAC has been shown to affect cysteine/cystine and glutathione/glutathione disulfide (GSH/GSSG) redox couples in blood, as well as levels of glutamate, glutamine and possibly, GABA. Measurement of these indices may inform the possible mechanisms of action of oral NAC (e.g., rebalancing key redox metabolites and/or excitatory/inhibitory amino acids) that may be relevant in the treatment of SIB in children with ASD.

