The statistician, [name], will conduct initial analyses to inspect data for errors, frequency, pattern, time to drop out, and missing data. This will include examination of frequency tables and dot plots for univariate data and scatter plots as needed. Data anomalies and outliers will be identified and addressed in coordination with the PI and data manager. Descriptive statistics will be calculated at baseline and follow-up time points using means and standard deviations, medians and interquartile ranges, or frequencies and percentages as appropriate.

Aim #1: As noted above, the primary aim of this pilot trial is feasibility. We set forth several benchmarks: a) demonstrate capacity to screen 2 subjects/month (in order to average 1.75 randomize subjects/month); b) no more than 15% attrition rate (e.g., no more than 2 of 14 randomized subjects); c) at least 70% compliance with study medication (determined by tablet counts and drug dairies); d) at least 80% collection of essential outcome measures (actual ratings ÷ expected X 100); e) at least 80% of parents will *agree* or *strongly agree* when asked in an anonymous survey that they would recommend the study and the study treatment to other parents of children with ASD and SIB.

Aim #2: 75% positive predictive value (PPV = screen positive and true cases ÷ all positive screens) for our screening method to classify children with automatically maintained self-injurious behavior.

Aim #3: The use of placebo-control in this trial permits blinded assessment. These benchmarks will be examined **within** the NAC group.

- a) Test for significant decline from baseline to Week 9 on the parent-rated Aberrant Behavior Checklist Irritability subscale using a paired t-test.
- b) at least 50% decline (on average) from baseline to Week 9 in the number of SIB events in children treated with NAC when counted by a trained technician who is blind to treatment assignment.

In addition to percent change, we will run ANCOVAs on these outcomes within the NAC group and across treatment groups with baseline values in the model.

c) at least 50% of the subjects randomized to NAC on will be rated *much improved* or *very much improved* on the Improvement scale of the Clinical Global Impression by a clinician blind to treatment assignment.

The other outcomes listed in Table 2 above (Parent Daily Checklist, CYBOCS-ASD) will be performed as exploratory outcomes.

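### Aim 3's preliminary-efficacy benchmarks are judged in the NAC arm alone; report the placebo result beside each one, above all for CGI-I response, where no between-arm comparison is named (minor)

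*Combined protocol and SAP*

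**What the plan says.** Specific Aims, Aim #3 lists three criteria under the label "Preliminary efficacy benchmarks within the NAC group", and Data Analysis, Aim #3 repeats that they are examined within that group:

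- (a) ABC Irritability: "Test for significant decline from baseline to Week 9 on the parent-rated Aberrant Behavior Checklist Irritability subscale using a paired t-test".
- (b) SIB events: an average fall of at least 50% from baseline to Week 9.
- (c) CGI-I: at least half of the NAC children rated much or very much improved.

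The limits are disclosed. Aim #3 states: "This sample size is not sufficient to test the superiority of NAC over placebo". The feasibility section opens with "Pilot studies are not about efficacy".

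Between-arm analyses do exist. After (a) and (b), and before (c), Data Analysis adds: "we will run ANCOVAs on these outcomes within the NAC group and across treatment groups with baseline values in the model". The direct-observation text says that change in counts and severity "within the NAC group (paired t test) and across treatment groups (ANCOVA) will be used to evaluate preliminary efficacy". Data Analysis, Aim #4 repeats across-group ANCOVAs for direct observation. None of these is attached to a benchmark.

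On the CGI-I, the outcome section says "The CGI-I will be used to assess overall response to treatment". Table 2.0 schedules responder status at Week 9, and Endpoint and Disposition uses positive response to decide what placebo children are offered. No analysis of responders other than the NAC threshold is named.

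**The concern.** A before-after criterion in one arm is met by whatever moves that arm. Children selected for troublesome behaviour may improve on re-measurement, parents who hope for benefit may rate more favourably, and nine weeks pass. If placebo children improve as much, the benchmark is still met, and the plan does not say how to read it in that case.

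The ABC and CGI-I benchmarks are also not independent: "Using available information (ABC scales, Parent Target Problems, Parent Daily Rating), the CGI-I will be rated by a blinded independent evaluator". A shift in parent report that has nothing to do with the drug can push (a) and (c) the same way.

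At stake is how a secondary aim is reported when the pilot is used to argue for a larger trial. The primary aim, feasibility, is not affected.

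**Working it through.** **The plan's own figure.** There is no power, alpha or effect-size statement for Aim 3 to reproduce. The total of 14 agrees only with the accrual plan: Months 2 to 9 are 8 months, and 8 × 1.75 = 14.

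**Inputs from the documents.** 7 per group (Data Safety and Monitoring Plan); 1:1 allocation (Design); benchmarks as above.

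**Inputs assumed.** Two-sided alpha 0.05; non-drug change of 0.3, 0.5 or 0.8 SD of the change score; non-drug CGI-I response of 20%, 30% or 40%.

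**Benchmark (a), no drug effect.** The paired t-test with n = 7 has 6 df and critical value 2.447, so the observed mean fall must be at least 2.447/√7 = 0.92 SD of the change score. The chance of this is P(T > 2.447), where T is noncentral t with 6 df and noncentrality d√7.

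| Non-drug change d | n = 7 | n = 6 completers |
|---|---|---|
| 0.3 SD | 9.9% | 8.8% |
| 0.5 SD | 20.0% | 16.9% |
| 0.8 SD | 42.8% | 35.6% |

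**Benchmark (b).** The documents give no mean or SD for SIB counts, so no probability is offered here. The logic is the same.

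**Benchmark (c), no drug effect.** 3/7 = 43% fails and 4/7 = 57% passes, so the chance is P(X ≥ 4), X ~ Binomial(7, p).

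- p = 0.20: 3.3%
- p = 0.30: 12.6%
- p = 0.40: 29.0%

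**What between-arm estimates would look like at 7 per arm.**

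- ABC Irritability or SIB counts: the unadjusted 95% half-width is t(0.975, 12) × √(2/7) = 2.179 × 0.535 = 1.16 SD. With ANCOVA it is about t(0.975, 11) × √(1 − r²) × √(2/7), which is 1.02 SD at a baseline-to-Week 9 correlation of 0.5 and 0.84 SD at 0.7. Simulation that includes chance baseline imbalance gives 1.04 and 0.86 SD.
- CGI-I: 4/7 v 2/7 is a difference of 2/7 = +29 points, with exact unconditional score 95% CI of about −29 to +74. With 4/7 on NAC, this interval excludes zero only if placebo has 0/7 (+8 to +90); against 1/7 it is −11 to +81.

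**Do those intervals tell effect from no effect?** Only weakly. Among trials that meet (c), the CI fails to favour NAC in 79% when both arms respond at 20%, and still in 74% when the true rates are 50% v 20%. Among trials that meet (a), the ANCOVA CI fails to favour NAC in about 91% (drift 0.5 SD) to 95% (drift 0.8 SD) with no effect. With a true effect of 0.5 SD of the Week 9 score and the same drift, it still fails in roughly three-quarters to four-fifths.

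**The case against.** The strongest reply is that the choice is deliberate and stated. The protocol says superiority cannot be tested, that randomization serves feasibility and blinded assessment, and that pilots are not for efficacy. Little room is left to read a met benchmark as superiority. All of that stands, and it is why the point is minor.

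A reader might infer that the plan contains no between-arm analysis. It does: ANCOVAs cover ABC Irritability and SIB counts, and the direct-observation text ties the latter to preliminary efficacy. For (a) and (b) the gap is only that nothing links those results to the benchmark.

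For (c), one could say that the longitudinal models for secondary measures in Data Analysis, Aim #4 cover the CGI-I. They concern scores on measures that are not listed, and they do not compare responder proportions. Placebo responder status is established anyway, so what is missing is one reporting line. Small numbers did not prevent a planned Fisher's exact test of adverse events across arms.

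A reader might also infer that a between-arm interval would settle whether NAC works. The figures above do not support that: at 7 per arm it usually includes zero whether or not there is an effect.

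Finally, the sizes rest on assumed drift and response rates. That is correct; they are ranges, not predictions.

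**Conclusion.** The point holds as a minor, inexpensive improvement to a secondary aim. The three benchmarks are within-arm, the planned ANCOVAs feed none of them, and CGI-I response has no named between-arm comparison. If the assumed non-drug change is present and NAC does nothing, (a) is met in about 10% to 43% of trials and (c) in about 3% to 29%.

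The documents do not support a stronger conclusion, such as that the plan intends to claim efficacy from one arm or that the benchmarks must be replaced. They can stay as written, provided each is read beside the placebo result.

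**What to change.** Keep the benchmarks and planned tests. After (c), in both Specific Aims, Aim #3 and Data Analysis, Aim #3, add:

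> Each benchmark quantity will also be reported for the placebo arm, with the NAC-minus-placebo difference at Week 9 and its 95% CI: from the planned baseline-adjusted ANCOVA for ABC Irritability and SIB counts, and as a difference in CGI-I responder proportions with an exact unconditional score CI. These are estimates, not tests of superiority. A met within-arm benchmark will be interpreted beside the placebo result and will not by itself be described as evidence of a drug effect.

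The interval method is named because the choice matters at this size: for 4/7 v 0/7 the unconditional score interval excludes zero, while Fisher's exact test gives p = 0.070.

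The cost is one paragraph, with no extra data, visits or children. The drawback is wide intervals, which should be presented as a statement of uncertainty.

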Investigational Pharmacist ([name]). The allocation pattern will be concealed to investigators. [name] will receive a form via email from the coordinator indicating that the subject meets entry criteria and he will assign the subject to NAC or placebo according to the permuted block.

Each subject will be followed by two blinded clinicians. The treating clinician ([name], CPNP) will monitor adverse events and manage the dose of the study medication. The independent evaluator will assess therapeutic response and will not discuss adverse events or medication dose with parent and child.

Figure 1. Study design

Dosing Active NAC and matching placebo will have identical appearance, odor, and taste. The effervescent tablet formulation of NAC and matching placebo will be supplied by BioAdvantex Pharma Inc. from Ontario, Canada (see attached letter from the company).

Participants will start with a single dose of 900mg once daily for one week. At Day 7, parents (primary caregiver) and subjects will return to Marcus for adverse event review. In the absence of dose limiting adverse events attributable to the study drug, the dose will be gradually increased (Day 8) to 900 mg twice a day. If

Table 1. NAC dose schedule for 9-week study in mg

Study Day 1-7	900 QD	Study Day 8-28	900 BID	Study Day 29 -63	900 TID
---------------	--------	----------------	---------	------------------	---------

this dose is well-tolerated, the dose will be increased to 900 three times per day. This dose schedule is adapted from the NAC trial in children with ASD (Hardan et al. 2012). This dose schedule serves as a guide and is not fixed. The treating clinician ([name], CPNP) can delay a scheduled increase or reduce the dose to manage an adverse effect at any time.

The treatment mask will be broken at Week 9 by [name] (Director of the Severe Behavior Clinic) who will not be involved in management of participants during the trial. [name] will follow placebo non-responders in the Open-label trial. She will remain blinded to the results of those subjects randomized to NAC. The independent evaluator, [name], will remain blinded.

Aim #1 [Feasibility]

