
Aim # 3 [Preliminary Efficacy]

Study outcome measures are listed in Table 2. All outcomes including direct observation of behavior in the laboratory setting, parent ratings of behavior and assessment of overall improvement will be collected blind to treatment assignment. Here we describe the outcome measures that are directly related to preliminary efficacy benchmarks (see Appendix A for detailed description of other outcome measures).

Aberrant Behavior Checklist (ABC) is a 58-item, informant-based scale with five subscales: *I. Irritability* (includes agitation, aggression and self-injurious behaviors, 15 items); *II. Lethargy* (includes social withdrawal, 16 items); *III. Stereotypic Behaviors* (7 items); *IV. Hyperactivity*, 16 items (includes overactivity and impulsiveness); and *V. Inappropriate Speech* (4 items). The ABC has been used as an outcome measure in many studies of children with ASD (RUPP Autism Network, 2002; RUPP Autism Network, 2005; Aman et al., 2009; Hardan et al., 2012; Bearss et al., 2015). In this proposed study, the parent-rated Irritability subscale will be of particular interest because it includes items on SIB. We will also be interested in the Stereotypy subscale.

Direct observation of the frequency and severity of SIB will also be collected at baseline and endpoint at the conclusion (but separate from) of the functional analysis. Operational definitions will be created for each child based on the parental description of the SIB. For example, if the child engages in hand-to-head hitting, the operational definition may be anytime the child's hand comes in contact with the head from a distance of 6-inches or greater. Similarly, for a child who engages in hand-biting the definition may be when the child's teeth make contact with the hand. Frequency data will be collected for any discrete behavior (such as head banging) and duration data will be collected for behaviors that

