Endpoint and Disposition As shown in Table 2, we will conduct a detailed set of outcome (direct observation, parent ratings, clinician ratings) and safety measures (Adverse Event Review, routine labs). [name] will train the independent evaluator to rate overall response on the Improvement item on the Clinical Global Impression scale (CGI-I). The child and

parent(s) will meet with [name] (Director of the Severe Behavior Clinic), who will break the blind and discuss the next steps in the child's treatment plan (see Figure 1). Children who show a positive response to NAC can continue with the treatment with the over-the-counter product. Children who were on placebo and did not show a positive response will be offered open-label NAC using the same study procedures. Children who did not show a positive response to NAC or those who showed a positive response to placebo will be advised on a case by case basis.

Data Management

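### Does the 50% average decline in SIB events need an averaging formula written into the plan?

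*Combined protocol and SAP*

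**What the plan says.** Specific Aims (Aim #3) and Data Analysis (Aim #3) state benchmark (b) in the same words: "at least 50% decline (on average) from baseline to Week 9 in the number of SIB events in children treated with NAC". Neither place gives a formula.

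The surrounding text points both ways:
- Data Analysis mentions percent change without saying whether it is per child or for the group.
- The Direct observation text under Aim #3 [Preliminary Efficacy] puts a paired t-test and ANCOVA on change in counts, which leans toward a group mean.
- The general descriptive summaries are to be given "using means and standard deviations, medians and interquartile ranges, or frequencies and percentages as appropriate". That sentence covers summaries by time point, not this benchmark.

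On what is counted, Direct observation records discrete acts by frequency, and records by duration those that "may occur for longer periods of time (such as hand biting". It then has a blinded rater tally counts during five 10-minute conditions.

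On status, Specific Aims says: "This sample size is not sufficient to test the superiority of NAC over placebo". Aim #1 [Feasibility] adds that a pilot is not about efficacy. The Data Safety and Monitoring Plan gives 7 children per group.

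On unblinding, Approach (Dosing) says: "The treatment mask will be broken at Week 9". Endpoint and Disposition has each family meet the clinic director, "who will break the blind and discuss the next steps".

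**The concern.** Benchmark (b) is the only efficacy benchmark that rests on directly observed behaviour; (a) is a parent rating and (c) a clinician's global rating. It carries a numerical pass line, yet two ordinary readings of the average can give different verdicts on the same seven children. A child's decline cannot exceed 100% but a rise has no limit, so the mean of individual percents is pulled toward failing. The group mean is dominated by the child with the highest rate.

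Assignments are revealed family by family from Week 9. In principle, then, the statistic could be picked once some NAC results are known. And if a hand-biter's behaviour is recorded only as duration, that child would seem to have no event count for the benchmark. At stake is how far a reader can trust a statement that the pilot met its observed-behaviour target.

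**Working it through.** **Inputs.** The threshold (50%), 7 NAC children and a 50-minute session (5 × 10 minutes) come from the plan. The plan gives no SIB rates, standard deviations or derivation of the 50% line, so there is no figure to reproduce. All counts below are hypothetical.

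**The two readings.** Let B and W be a child's baseline and Week 9 counts.
- R1 = mean over children of (W - B)/B
- R2 = (sum of W)/(sum of B) - 1

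R2 is the average of the same per-child percent changes, weighted by B. The two agree when baselines are equal, and part when percent change goes with baseline level.

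**Can the verdicts split?** Yes, in both directions.

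| Seven children | R1 | R2 |
|---|---|---|
| Six 40→10, one 10→40 | (6 × -75 + 300)/7 = -21.4%, not met | 100/250 - 1 = -60%, met |
| One 600→240, six stay at 20 | -60/7 = -8.6%, not met | 360/720 - 1 = -50%, met |
| Baseline 20, 25, 30, 35, 40, 50, 400; Week 9 6, 8, 9, 10, 12, 15, 320 | -62.8%, met | 380/600 - 1 = -36.7%, not met |

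**How often?** This depends wholly on assumptions.
- Model 1: every child has the same true fall, with independent log-normal noise in each session (log-SD s = 0.3 to 0.8), Poisson counts, and between-child log-SD 0.3 to 1.5. R1 and R2 disagree in roughly 15 to 40% of trials at a true 60% fall and 2 to 36% at 70%. At s = 0.2 the figures are 7 to 22% and 0.2 to 4%.
- Model 2: log-normal baselines (log-SD 0.5 to 1.5) and independent log-normal Week 9/baseline ratios (median 0.4 or 0.5, log-SD 0.5 or 1.0). Disagreement is 7 to 25%.

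**What would choosing afterwards buy?** Under model 1 at a true 40% fall, short of the benchmark, R1 passes in 8 to 10% of trials, R2 in 17 to 39%, and whichever is better in 17 to 40%. Against R2, free choice adds only a few points in any one setting; against R1 it adds more. Where children's true responses differ, the gain over R2 is somewhat larger.

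**Would a median be better?** Take four children going 40→20 and three going 40→120.
- Median change: -50%, met.
- R1 = (4 × -50 + 3 × 200)/7 = +57%.
- R2 = 440/280 - 1 = +57%.

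The median passes an arm in which self-injury rose by more than half. At a true 40% fall under model 1 it passes 22 to 39% of trials, about as often as free choice between the two means.

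**Would log rates be better?** At a 50% fall, with widely differing baselines (log-SD 1.5, s = 0.3, no zeros), power rises from 24% on raw counts to 79%. With similar baselines (log-SD 0.3, s = 0.3) and 15% zero sessions, it falls from 86% to 64%, and to 55% or 40% as the constant added for zeros drops from 1 to 0.5 or 0.1.

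**Events and durations.** The hand-biting example in Direct observation defines the act as the moment the "teeth make contact with the hand", which is countable. The sentence on real-time tallying makes no exception for duration-coded behaviours. The Functional Analysis text under Aim #2 expresses SIB as counts per minute, and every randomised child must go through that analysis. It is a separate session, so this is supporting evidence rather than proof.

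**The case for a change.** The best case for a change is that a pass line should be scorable in only one way. The same Data Analysis section gives explicit formulas for outcome-collection completeness and for positive predictive value, and a named test for benchmark (a); benchmark (b) has neither. A sentence would cost almost nothing, and blinding of the rater protects the counts but not the choice of summary.

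Most of this is true. The formula is missing, the verdicts can split, and no nearby text settles the matter.

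What does not stand is the weight placed on it. No go/no-go rule, error rate or sample size depends on the result. The clinic director who breaks the mask takes no part in managing participants during the trial, and the independent evaluator stays blinded; nothing says the statistician learns assignments child by child. Nor would a formula remove the fragility of seven children, since under each summary examined the verdict can turn on one child.

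**Conclusion.** No change follows. This is missing detail of the kind an analyst fills sensibly. Both means are legitimate, and the tests on change in counts lean toward the group mean without settling it. Seven pairs of rates fit in one small table from which either statistic can be worked out.

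The possibility of opposite verdicts is certain arithmetic. Its frequency is unknown, and the ranges from 7 to 25% up to 15 to 40% reflect assumed variability and nothing in the plan. The consequence is confined to how one descriptive benchmark in a feasibility pilot is worded in the report.

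The median and log-rate alternatives are trade-offs with no clear gain. The event-versus-duration question is a clarification: the most natural reading is that onsets are tallied for every child.

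This conclusion rests on the benchmark staying descriptive. If a formal decision to proceed were tied to the 50% line, a single formula would be needed.
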